### 8.4 Handling of Missing or Incomplete Dates

#### Imputation rules for missing or partial adverse event start/stop dates

- If the AE end date day is missing (month and year provided) then set the date to the last day of the month.

## Statistical Analysis Plan (SAP)

---

- If the AE end date month is missing (day and year provided) then set the date to the latest calendar month consistent with the day.
- If the AE end date day and month are missing (year is provided) then set the date to December 31.
- If the year of the AE start date or AE end date are missing, then a query to the site must be made to gather additional information.
  - If the start date is completely missing, then set the start date to the date of first dose. If the end date is completely missing, then set the end date to the date of last follow-up.
  - If the start date day is missing (month provided), then set the date to the first of the month, unless the month and year are the same as the month and year of first dose. In this case, set the date to the date of first dose. If the end date day is missing (month provided), then set the date to the last day of the month.
  - If the start date month is missing (day provided), then set the month date to January, unless the day and year are the same as the month and year of first dose. In this case, set the date to the date of first dose. If the end date month is missing (day provided), then set the date to the latest calendar month consistent with the day.
  - If the start date year is missing (day and month provided), then set the year to the year in which the subject was first screened, unless the day and month are the same as the day and month of first dose. In this case, set the date to the date of first dose. If the end date year is missing (day and month provided), then set the date to the latest calendar year in which the subject is followed.

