### 9.10 Analysis of Study Endpoints

#### 9.10.1 Primary Endpoint 1a – Adverse Events, Cohorts 1-4

In order to evaluate primary objective #1, to evaluate the safety and tolerability of repeat intramuscular (IM) administration of G03-52-01 in healthy adult subjects, primary endpoint #1a will be used:

The occurrence of adverse events (AEs) and serious adverse events (SAEs) following administration of G03-52-01 to the final visit

Adverse events (AEs) will be captured in a log at all scheduled visits from Baseline/Dosing [Visit 2 (Day 1)] through the end of study. Unless specified otherwise, AEs summaries will include all events starting from the date of initial administration of G03-52-01 up to and including the date of each subject’s final scheduled

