Finally, three AE tables will be produced combining data across all four cohorts with the goal of comparing AE rates following initial administration of IP and before subjects in the first three cohorts received their second dose. For Cohorts 1-3, all AEs will be included that occur starting from the date of initial administration of G03-52-01 and prior to the date of each subjects' second dose. For Cohort 4, all AEs will be included that occur starting from the date of initial administration of G03-52-01 and prior to the date each subject's Day 45 study visit. If a Cohort 4 subject does not attend their Day 45 study visit, then all AEs will be included that occur up to and including 44 days from the subject's initial administration of G03-52-01. For these three AE summaries, Cohort 1 and Cohort 2 subject groupings will include both DP lots and the two Placebo groups (Cohorts 3 and 4) will be pooled together, such that the treatment groupings are as follows: Cohort 1, 50 mg (Both Lots); Cohort 2, 100 mg (Both Lots); Cohort 4, 100 mg; Cohorts 3 and 4, Placebo; and

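### SAP 8.4 sets no floor at first dose for imputed AE start dates: the missing-year rule, and on some readings the missing-month rule, can push a post-dose event out of the primary AE tables

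*SAP*

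**What the plan says.** SAP 8.4 gives separate start-date rules according to which part is missing:

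- **Day missing:** "then set the date to the first of the month, unless the month and year are the same as the month and year of first" administration; the first-dose date then applies.
- **Month missing:** "If the start date month is missing (day provided), then set the month date to January", with the exception "unless the day and year are the same as the month and year of first dose".
- **Year missing:** "then set the year to the year in which the subject was first screened", with the exception "unless the day and month are the same as the day and month of first dose".
- **Date wholly missing:** the first-dose date is used.

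These rules are indented under an instruction for a missing year: "a query to the site must be made to gather additional information".

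SAP 9.10.1 (Primary Endpoint 1a) then selects by date: "AEs summaries will include all events starting from the date of initial administration of G03-52-01", up to the final scheduled visit. The three cross-cohort tables for the first 45 days have the same lower bound. In the two-dose cohorts the window reads: "all AEs will be included that occur starting from the date of initial administration of G03-52-01 and prior to the date of each subjects' second" administration. All AEs in the database still go into the listings. Protocol 9.9.1 starts AE collection on Day 1, during and after dosing.

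**The concern.** An AE in this database has, by the collection rule, started on or after the day of first dose. An imputed start earlier than that is therefore wrong, and the filter in SAP 9.10.1 acts on the imputed date. The event would leave the tables for Primary Endpoint 1a because of a date convention.

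The error runs in the anti-conservative direction and conflicts with the rest of SAP 8.4. An event with no start date at all is placed on the day of first dose and counted. An event with a known day and month but no year can be placed months before dosing and not counted. The wholly-missing and day-missing rules both protect against this; the year rule does not, and the month rule does so only if its exception means something other than what it says.

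**Working it through.** The plan states no figure to reproduce, so the check applies the rules as written.

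**Inputs from the documents.** Follow-up L is 240 days in Cohorts 1-3 and 120 days in Cohort 4 (protocol synopsis). Screening is up to 14 days before dosing (protocol Appendix A).

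**Assumptions.** First doses are spread evenly over one calendar year of N days (2022, N = 365, for Cohorts 1-3; 2024, N = 366, for Cohort 4). Onsets are spread evenly over follow-up. Screening is s = 1, 7 or 14 days before dosing.

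**Readings of the January exception.** (A) AE day and year equal the day and year of first dose. (B) Literal: AE day number equals the first-dose month number, and the years match. (C) A matching year is enough.

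Enumerating every first-dose date against every onset day gives the share of post-dose AEs placed before first dose, given that the part is missing:

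| Part missing | Case | Cohorts 1-3 | Cohort 4 |
|---|---|---|---|
| Year | s = 1 | 33.0% | 16.5% |
| Year | s = 7 | 34.6% | 18.1% |
| Year | s = 14 | 36.6% | 20.0% |
| Month | Reading A | 60.9% | 76.8% |
| Month | Reading B | 60.8% | 76.8% |
| Month | Reading C | 0% | 0% |
| Day | as written | 0% | 0% |

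**Year rule by hand.** An AE is sent back if it falls in the year after dosing, average chance (L - 1)/(2N), or if the subject was screened in December and dosed in January, chance s/N.
- Cohorts 1-3, s = 1: 239/730 + 1/365 = 0.327 + 0.003 = 0.330.
- Cohort 4, s = 1: 119/732 + 1/366 = 0.163 + 0.003 = 0.165.

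**Month rule, Reading A, by hand.** Start from AEs in the dosing year. Subtract January doses where the imputed January date is not before dose, about (31/365)/2 = 0.042. Subtract day matches, about 1 in 30.4.
- Cohorts 1-3: 0.673 - 0.042 - 0.022 = 0.609.
- Cohort 4: 0.837 - 0.042 - 0.028 = 0.767.

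**Dependence on the dosing calendar.** For one subject the year rule ranges from nothing to nearly everything. Dosed on 1 February and screened that year, 240 days of follow-up end in September, so the share is 0%. Dosed on 31 December, 239 of 240 onset days fall in the next year, so it is 99.6%.

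**Hypothetical cases.**
- Screened 5 Sep 2022, dosed 15 Sep 2022, AE 10 Feb 2023 (Day 149), year missing: imputed 10 Feb 2022, 217 days before dose.
- Cohort 4, screened 20 Sep 2024, dosed 1 Oct 2024, AE 15 Jan 2025 (Day 107), year missing: imputed 15 Jan 2024, 260 days before dose.
- Cohort 4, dosed 10 Jun 2024, AE 20 Jul 2024 (Day 41), month missing, Reading A: imputed 20 Jan 2024, 142 days before dose.

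**The case against.** The strongest reply is that this will seldom happen and that the January half may be only a copying slip. Protocol 9.10.1 records a start date and time for every AE, AEs are reviewed at each scheduled visit, and SAP 8.4 requires a site query when the year is missing. The day-missing rule, probably the one used most, is properly guarded. The January exception resembles that rule with one word changed; if a year match was meant, it places no event before dose. Listings keep every AE. SAP 9.10.1 also says that AEs occurring after study medication began are included in the summaries, which could be read as keeping a known post-dose event. Finally, the rule is the same in every arm and no hypothesis is tested.

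Most of this stands as a limit on size. It does not remove the defect. The query comes before imputation and does not correct a date imputed after an unsuccessful query. The general inclusion sentence gives no tie-break against a filter that works on start date. The year rule fails on its plain wording, whatever the January exception was meant to say.

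A reader might infer that 61% or 77% of events with a missing month are certain to be lost, or that most events with any partial date are. The documents do not support that: the month figures fall to 0% under Reading C, and the year figures are minorities. Nor do they support saying that the events vanish, since the loss is from tables only.

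**Conclusion.** The concern holds in limited form. SAP 8.4 does not floor imputed AE start dates at first dose. Given a missing year, about 33-37% of AEs in Cohorts 1-3 and 17-20% in Cohort 4 would be dated before first dose. Given a missing month, the share is about 61% and 77% under Readings A and B, and 0% under Reading C; the text does not settle which applies.

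Every figure is conditional on the date part being missing and rests on evenly spread dosing and onset. The documents give no rate of partial dates, so the number of events cannot be estimated; it should be small. No material bias in AE rates is shown. The point is worth correcting because a stated rule gives a wrong result for the primary safety endpoint, where one serious or related event missing from a table can matter, and because the repair is cheap.

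**What to change.** Replace the month-missing and year-missing start rules in SAP 8.4 with one: impute the earliest date consistent with the known parts that is on or after first dose; if none exists, use the date of first dose. Delete the January exception. No separate clause for the second dose is needed: if the known parts already place the event after that dose, so does the earliest consistent date.

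- **Year missing.** The rule gives a single date, because follow-up is under one year. The first two cases above return to 10 Feb 2023 and 15 Jan 2025, their true dates.
- **Month missing.** The third case becomes 20 Jun 2024 (Day 11) and is counted.
- **Downside to state.** With a missing month, a late event can move early. For a subject dosed 15 Sep 2022, with the second dose due on Day 45 (29 Oct), an AE on 20 Dec 2022 (Day 97) would be imputed to 20 Sep (Day 6). It would then count under Dose 1 and in the first-45-day tables. Flag imputed start dates in those tables.

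The same wording would cover a start date with only the year known, for which SAP 8.4 now has no rule.

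The cost is one sentence in SAP 8.4, a small program change and a table footnote. If the SAP is not reissued, the change can be reported in the CSR as a deviation, as the SAP Introduction provides.

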### Imputation rules for missing or partial prior/concomitant medication start/stop dates

- Start dates will not be imputed.
- Partial stop dates of prior/concomitant medications will be assumed to be the latest possible date consistent with the partial date. If day, month, and year are missing, then assign 'continuing' status to the stop date.

## Statistical Analysis Plan (SAP)

---

### 9 Statistical Methods

#### 9.1 General Statistical Conventions

All statistical procedures will be completed using SAS version 9.4 or higher.

Unless otherwise stated, all statistical testing will be two-sided and will be performed using a significance (alpha) of 0.05. Two-sided 95% confidence intervals (CI) will be provided where relevant.

Continuous variables will be summarized using descriptive statistics, including number of subjects (n), mean, median, standard deviation (SD), first quartile (Q1), third quartile (Q3), minimum, and maximum. Means, medians, and quartiles (if averaged value) will be rounded to one more decimal place than what is reported in the data. SDs will be rounded to two more decimal places than what is reported in the data.

For categorical variables, summaries will include counts of subjects and percentages. Percentages will be rounded to one decimal place.

For summary purposes, baseline is defined as the last measurement prior to the first treatment administration. All summaries will be presented by treatment group and for all subjects, unless otherwise specified.

All subject data, including those derived, will be presented in individual subject data listings. Unless otherwise stated, unscheduled visit results will be included in date/time chronological order within subject listings. All listings will be stratified by treatment group and sorted by subject ID in ascending numerical order, and date/time in ascending chronological order. The subject's race, sex, and age will be stated on each listing. Unless otherwise stated, data listings will be based on all randomized subjects (ITT Population).

#### 9.2 Subject Disposition

Subject disposition information will be summarized by treatment group and overall. The table summary will include the total number of screened subjects, as well as the frequency and percentage of subjects who were screen failures and those who re-screened, with the percentages being based on the total number of screened subjects. Additionally, the total number of subjects who were randomized, dosed with IP, and completed the study per protocol will also be summarized using counts and percentages, using the total number of enrolled subjects as the denominator for percentages. The primary reason for study discontinuation will also be tabulated, using the total number of randomized subjects as the denominator for the proportion calculation. Subject disposition will be listed along with inclusion or exclusion criteria that were not met for randomization. The counts and percentages of subjects in each analysis set will also be tabulated.

A separate table summary will display subject enrollment by site using counts and percentages. The summary will include the name of the investigator at the site.

Data to be included in subject disposition listings will include:

- End of study status for randomized subjects, including reason for discontinuation for discontinued subjects
- Screen failure reason(s) for subjects who failed at screening
- Re-screened and re-consented subjects, along with any associated collected laboratory data

Treatment misallocations occur when a subject receives a different treatment than to what they were randomized. In these cases:

- If a subject were randomized but not treated, the subject will be included according to their randomized study arm assignment in the subject disposition summaries. The subject will be included in the ITT population only.
- If a subject were treated but not randomized, the subject will be excluded from the trial.
- If a subject were randomized but received a different treatment regimen, then the subject will be included according to their randomized study arm assignment in the ITT population but will be excluded from the PP population. The subject will be included according to the treatment regimen actually received for all safety analyses using the Safety population.

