11.4. Analysis Populations

Analysis populations for statistical analyses include intent-to-treat (ITT), safety, per-protocol (PP) and PD and PK populations as shown in [Table 1](#).

Table 1: Analysis Populations

Population	Description
Intention-to-Treat (ITT)	All subjects who were randomized. They will be analyzed according to the treatment group to which they were randomized.
Safety	All randomized subjects who received any study drug. They will be analyzed according to the treatment they actually received.
Per-Protocol (PP)	All subjects in the ITT population who have received all planned study drug, have no major excluding protocol deviations and will be analyzed according to the group to which they are randomized.
Pharmacodynamic (PD)	All Safety population subjects who have sufficient evaluable PD result following dosing. They will be analyzed according to the treatment they actually received.
Pharmacokinetic (PK)	All Safety Population subjects who have sufficient evaluable PK result following dosing.

	They will be analyzed according to the treatment they actually received.
--	--

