### 7 Analysis Populations

#### 7.1 Description of Analysis Populations

##### 7.1.1 Intention-to-Treat (ITT) Population

The ITT population includes all subjects who are randomized. Subjects in this population will be analyzed according to their randomized treatment assignment.

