##### 7.1.2 Safety Population

The Safety population includes all subjects in the ITT population who receive at least one dose of IP. Subjects in this population will be analyzed according to the actual treatment received.

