**Table 3: Derived Variables**

Variable	Formula
Demographic and Baseline Characteristics	
Body Mass Index	weight (kg) / [height (m)] 
Age	Calculated at the time of informed consent. Sample SAS code to calculate age is: age = floor((informed consent date - date of birth)/365.25)
Baseline	Baseline is defined as the last measurement prior to the first treatment administration
Derivation of Durations	
Study day at any visit	date of visit – date of first dose. One day is added if the difference is ≥ 0.
Duration of any events	end date of event – start date of event + 1
Other Derivations	
Incidence in a group	The proportion of the participants experiencing the outcome of interest compared to the total number of participants at risk of experiencing the outcome of interest. (e.g., the incident rate of SAEs after injection are the number of participants with an SAE reported after injection divided by the number of participants that received the injection).
Pharmacodynamic (PD) Parameters	
AUC (0-t)	Area under the concentration time-curve from the time of dosing to the time of the last measurable (positive) concentration
C max	Maximum observed concentration, occurring at time T max .
T max	Time of maximum observed concentration. For non-steady-state data, the entire curve is considered. If the maximum observed concentration is not unique, then the first maximum is used.
t 1/2	Terminal half-life defined as ln(2)/ λ z as measured during steady-state
Pharmacokinetic (PK) Parameters	

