## Statistical Analysis Plan (SAP)

---

Total. The number of AEs and the number and percentage of subjects that experienced the given AE will be summarized by the above mentioned treatment groupings.

The three AE summaries will consist of:

- Overall Summary of Adverse Events within First 45 Days of Initial Administration of IP
- Adverse Events within First 45 Days of Initial Administration of IP by System Organ Class, Preferred Term, and Maximum Severity
- Adverse Events within First 45 Days of Initial Administration of IP by System Organ Class, Preferred Term, and Closest Relationship to Study Medication

Unless otherwise specified, at each level of subject summarization of AEs, a subject will be counted once, even if they reported more than one event. If more than one occurrence of an event is reported, the event of the worst severity or the worst-case relationship assessment will be summarized. In summaries by SOC and PT, adverse events will be sorted in descending frequency by SOC and PTs within each SOC according to the total number of events among all subjects.

All AE summaries will be presented for the Safety population.

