## Statistical Analysis Plan (SAP)

---

displayed in a separate listing. Symptom-directed physical examinations can be performed at any visit, scheduled or unscheduled.

Unscheduled visit data for all safety analyses will be presented in listings but not included in table summaries, with the exception that an unscheduled visit result will serve as a subject's baseline result if it is their last result prior to first treatment administration.

All safety analyses will be presented for the Safety population.

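### A subject dosed without being randomised would be missing from every AE and safety summary table for the primary safety endpoint (SAP 9.2 and 7.1.2)

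*SAP*

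**What the plan says.** SAP 9.2 gives three rules for treatment misallocation. A subject randomised but not treated stays in ITT only. A subject randomised but given a different regimen is analysed by regimen received for safety. For the remaining case the rule is: "If a subject were treated but not randomized, the subject will be excluded from the trial".

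The analysis sets point the same way. SAP 7.1.1: "The ITT population includes all subjects who are randomized". SAP 7.1.2: "The Safety population includes all subjects in the ITT population who receive at least one dose of IP". Protocol 11.4, Table 1, defines the Safety population as: "All randomized subjects who received any study drug".

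The primary safety endpoints rest on that population. SAP 9.10.1 (Endpoint 1a): "All AE summaries will be presented for the Safety population". SAP 9.10.2 (Endpoint 1b): "All safety analyses will be presented for the Safety population".

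**The concern.** Primary Endpoint 1a is defined by exposure: "The occurrence of adverse events (AEs) and serious adverse events (SAEs) following administration of G03-52-01 to the final visit". SAP Table 3 illustrates incidence with SAEs after injection, where the count of participants with an SAE is "divided by the number of participants that received the injection". A person injected outside the randomisation system meets both descriptions, yet the rule removes that person from numerator and denominator alike.

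The rule also breaks with its neighbour in SAP 9.2, which analyses a wrongly treated subject by what was received. Only the unrandomised case departs from that principle.

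Safety data could exist for such a person, because Protocol 6.2 asks that subjects removed after dosing be followed for safety where possible. The SAP gives those data no place in a summary and promises no separate row or narrative. In a study of healthy adults with safety as a primary objective, one event can matter. Protocol 9.12.1 lists a single SAE definitely or possibly related to study product among the triggers for DSMB review.

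**Working it through.** The documents give no figure for this case, so there is none to reproduce. The check is a reading of the definitions, followed by an illustration of size.

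**Summary tables**

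1. The subject was treated but not randomised, so is not in ITT (SAP 7.1.1).
2. Safety is a subset of ITT, so the subject is not in Safety (SAP 7.1.2; Protocol Table 1 agrees).
3. AE summaries use Safety, so the subject is in no AE table (SAP 9.10.1).
4. The remaining safety analyses use Safety, so the subject is in no laboratory, vital-sign, ECG or examination table (SAP 9.10.2).
5. SAP 9.2 reaches the same result directly by taking the subject out of the trial.

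Steps 1 to 4 do not depend on step 5. Deleting the SAP 9.2 bullet alone would change nothing, because 7.1.2 would still exclude the subject.

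**Listings**

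- SAP 9.10.1 says that every AE held in the database is listed.
- SAP 9.1 bases listings on randomised subjects unless something else is stated.
- SAP 9.3 limits the deviation table, and the deviation and exclusion listings, to randomised subjects.
- SAP 9.2 removes the subject from the trial.

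SAP 9.10.1 can be read as the stated exception to 9.1, but the SAP does not say which prevails over 9.2. Listing is possible, not assured.

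**Illustration of size**

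Assumption: one treated but unrandomised subject has an event that nobody else in the group has. Group sizes are the expected numbers in SAP Table 1: 75 (one lot of one dose, or Cohort 3 placebo), 150 (one dose, both lots) and 200 (Cohort 4 active).

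- Subject omitted: 0/n, with upper limit of the exact two-sided 95% interval = 1 − 0.025^(1/n).
- Subject counted as treated: 1/(n+1), with the Clopper-Pearson 95% interval.

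| n | Omitted: rate (upper limit) | Counted: rate (95% CI) |
|---|---|---|
| 75 | 0/75 = 0% (4.80%) | 1/76 = 1.32% (0.03% to 7.11%) |
| 150 | 0/150 = 0% (2.43%) | 1/151 = 0.66% (0.02% to 3.63%) |
| 200 | 0/200 = 0% (1.83%) | 1/201 = 0.50% (0.01% to 2.74%) |

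The change in rate is small. What matters is that the table shows no such event when one occurred after dosing.

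**The case against.** The strongest case on the other side has four parts.

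**Other safety capture exists.** A reader might infer that the plan could hide a serious event. The documents do not support that. Protocol 9.10.2 requires all SAEs to be reported to pharmacovigilance within 24 hours of awareness and recorded in the CRF. The DSMB trigger in Protocol 9.12.1 for a related SAE is not limited to randomised subjects, and neither is SAE reporting. Protocol 14.5 requires the dosing error itself to be reported as a deviation. This objection stands: the gap is omission from summary tables, with uncertain listing, and not a failure to report.

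**The case is largely prevented.** Assignment runs through a central system (SAP 3.3), and the pharmacist prepares the dose from the assignment (Protocol 7.5). Protocol 3.1.3 says that Cohorts 1-3 had completed their last visit, so no new case can arise there, although the rule still governs how anyone already dosed that way is analysed. A reader might infer that some of the 625 planned subjects are affected. The documents report none and give no basis for a count. This stands too, and it limits the importance of the point.

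**The documents agree.** A reader might see a conflict between SAP and protocol. There is none on the Safety definition: SAP 7.1.2, SAP 9.2 and Protocol Table 1 all restrict it to randomised subjects. The tension lies between that definition and the exposure-based endpoint and incidence example.

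**Randomised comparisons stay clean.** Restricting Safety to randomised subjects keeps unrandomised people out of by-group displays. That is a real but weak advantage here. No formal testing is planned (SAP Section 6), the safety tables are descriptive, and SAP 9.2 already sets randomised assignment aside when a subject receives a different regimen.

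**Conclusion.** The point holds as a narrow one. As written, an AE or SAE in a subject dosed without randomisation would be left out of every AE and safety summary table for the primary safety endpoint. This follows from stated rules in both documents, not from a missing detail, and it sits badly with an endpoint and an incidence example based on administration.

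In the illustration, a displayed 0% would become about 0.5% to 1.3%, depending on the group. That range rests wholly on the assumption of one such subject with an otherwise unseen event. If no such subject exists, no result changes. The point is worth correcting because the correction is cheap, not because the case is likely.

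One limit on the evidence: the SAP is written to protocol v5.0 of 06-JAN-2025, while the protocol available is dated 12 Apr 2024. The wording of Table 1 in v5.0 could not be checked. The SAP part of the point does not depend on it.

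**What to change.** 1. **SAP 7.1.2:** define Safety as all subjects who received any study product, analysed by treatment received, without requiring ITT membership.
2. **SAP 9.2:** replace the bullet. Treated but unrandomised subjects are excluded from ITT and PP, included in Safety summaries by treatment received, identified by a footnote, and listed with a narrative. Say that this listing applies despite the default in SAP 9.1.
3. **SAP Section 10** (now N/A): record the difference from Protocol Table 1, after checking that table in v5.0. Recording it there avoids a protocol amendment for this point alone.
4. **SAP 7.1.4:** the PK and PD populations are drawn from Safety, so state whether they remain limited to randomised subjects. Otherwise the first change widens them too.

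The cost is a few sentences in the SAP and a footnote in the table templates, with no new data collection. The downside is that a rare unrandomised subject may enter a descriptive by-treatment safety table, which the footnote makes visible.
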